5.1.2 Secondary Endpoints

The secondary endpoints for this study will compare changes after 12 and 52 weeks of treatment to baseline for the following:

- Limb circumference
- Skin evaluation

In addition, changes after 24 and 52 weeks of treatment to baseline for the following parameter:

- QoL

To assess Flexitouch compliance, subjects will be categorized as noncompliant, partially compliant, or compliant (Table 1). Primary and secondary outcomes will then be compared across the defined compliance categories.

Table 1. Compliance Category Definitions

Compliance Category	Definition
Noncompliant	Prescribed care followed an average of 0-2 days per week.
Partially Compliance	Prescribed care followed an average of 3-4 days per week.
Compliant	Prescribed care followed an average of 5-7 days per week.

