7.10 Flexitouch Compliance Assessment & Subject Diary

At each phone call and clinic visit, subject compliance will be assessed by collecting the following information:

- Days Flexitouch used in past week
- Days compression garments used in past week
- Difficulty in following treatment
- Difficulty in putting on Flexitouch garments
- Difficulty using Flexitouch controller
- Pain or discomfort experienced when using Flexitouch
- Position treatment being done in

If the subject reports difficulty following treatment, putting on the Flexitouch garment, difficulty using the Flexitouch controller, or is experiencing pain or discomfort when using Flexitouch, the site may refer the subject to Tactile Medical clinical services for assistance in addressing the issue(s).

In addition, the subjects will be provided with a Subject Diary at their Screening/Baseline visit and be instructed to begin completing the diary when they start using their device after their training visit. The subject will be asked to keep a daily record of their use of Flexitouch, Actitouch (if prescribed), and compression stockings. (Appendix C) Subjects should bring their diary into each study visit for review and collection.

If the subject is noncompliant or partially compliant in device use, (see Table 1), the site should identify barriers to compliance and determine if additional device training by the site or Tactile personnel is warranted. If noncompliance continues, the Investigator may initiate the subject's withdrawal from the study.

At the 4 week in-clinic follow-up visit, if a subject is not using their Flexitouch an average of 3 times per week, they will be considered a screen failure.

If the subject experiences a complication (e.g., active infection, DVT) that requires temporary discontinuation of device use and 4 weeks of continuous treatment is not possible before the final in-clinic visit takes place, the subject should be withdrawn from the study.

Additionally, a device history log may be downloaded periodically from Flexitouch Plus units.

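### Section 5.1.2 compares outcomes only across three compliance bands; analysing average days per week as a number would use data already collected and usually has more power

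*Combined protocol and SAP*

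**What the plan says.** Section 5.1.2 states that "subjects will be categorized as noncompliant, partially compliant, or compliant (Table 1"), and then: "Primary and secondary outcomes will then be compared across the defined compliance categories". Table 1 defines the bands by three entries:

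- Noncompliant: "Prescribed care followed an average of 0-2 days per week"
- Partially compliant: "Prescribed care followed an average of 3-4 days per week"
- Compliant: "Prescribed care followed an average of 5-7 days per week"

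No other analysis relating compliance to outcome appears. Section 13.1 names no statistical method. Section 13.2 gives up to 300 subjects as a convenience sample, without a power calculation.

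Finer data are collected. Section 7.10 says: "The subject will be asked to keep a daily record of their use of Flexitouch", along with Actitouch where prescribed and compression stockings. Days of device use in the preceding week are also recorded at every phone call and clinic visit. The schedule in section 7.13 shows nine such contacts (weeks 1, 4, 8, 12, 18, 24, 32, 40 and 52).

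Two further statements in section 7.10 matter. It applies the bands to the device: "If the subject is noncompliant or partially compliant in device use, (see Table 1"). It also sets the week-4 rule: "if a subject is not using their Flexitouch an average of 3 times per week, they will be considered a screen failure". Exclusion criterion 15 and section 5.2.3 carry the same threshold.

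**The concern.** Compliance is a study objective (section 4.0) and a secondary endpoint in the synopsis. The band comparison is the only planned look at whether benefit follows the amount of use. Under Table 1 a 5-day and a 7-day subject count as the same, while two subjects just either side of a boundary count as different in kind. The documents give no rationale for the cut points.

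The week-4 rule removes many subjects who would fall in the lowest band, which leaves mainly a contrast of 3-4 with 5-7 days. A two-way split of a graded variable keeps less of its information than three well-filled bands.

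At stake are a real gradient that could be missed although the data would show it, and the lack of any estimate per additional day. The pre-post primary comparisons are not affected.

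**Working it through.** There is no stated power or derived sample size to reproduce, so the check compares analyses under stated assumptions.

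**From the documents.** Bands 0-2, 3-4 and 5-7 (Table 1); N up to 300 (section 13.2).

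**Assumed.** Two-sided 5%; an outcome that is linear in days with normal error; various shapes of use on 0-7 days. Averages between 2 and 3 or between 4 and 5 fall in no band, so cuts were placed at 3 and 5, or at 2.5 and 4.5.

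**Formulas.** Power comes from the noncentral F distribution with λ = N·R²/(1−R²).

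- Continuous average: R² = r², 1 df.
- Unordered bands: R² = r²·s, where s is the between-band share of the variance of days; 2 df with three occupied bands, 1 df with two.
- Trend across bands: R² = r²·corr(band, days)², 1 df.

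**Step 1, reference.** For 80% power at N=300 the continuous analysis needs r = 0.160: r² = 0.02566 and λ = 300 × 0.02566 / 0.97434 = 7.90.

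**Step 2, uniform use on 0-7, cuts at 3 and 5.** The band widths are 3, 2 and 2, so the within-band share is (27+8+8)/343 = 0.125 and s = 0.875. R² = 0.02244, λ = 6.89, and with 2 df the power is 64.3%, a loss of 15.7 points. A trend test on the same bands has about 74%, a loss of about 6.

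**Step 3, lowest band empty, uniform use on 3-7, cut at 5.** The within-band share is (8+8)/64 = 0.25 and s = 0.75. R² = 0.01924, λ = 5.89, and with 1 df the power is about 68%, a loss of about 12. A trend test on two bands is the same test, so it recovers nothing.

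**Step 4, other shapes (80% reference, cuts at 3 and 5).**

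| Assumed use | Bands occupied | Unordered power | Loss (points) |
|---|---|---|---|
| Uniform 0-7 | 3 | 64% | 16 |
| 7×Beta(5,2), mean 5 | 3 | 59% | 21 |
| Normal(5, 1.2), clipped | 3 | 57% | 23 |
| Uniform 3-7 | 2 | 68% | 12 |
| 7×Beta(5,2), 3 or more only | 2 | 65% | 15 |
| 7×Beta(8,2), 3 or more only | 2 | 60% | 20 |

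Over all eleven shapes tried with these cuts, the unordered loss was 11.9-27.6 points. With a trend test on three occupied bands it was 2.5-12.1.

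**Step 5, where the size changes.**

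- *Cuts at 2.5 and 4.5:* the unordered loss runs from 2.7 points (use in two tight clusters, lowest band nearly empty) to 44.4 (93% of subjects in the top band). The trend loss with three occupied bands reaches 17.5.
- *High reference power (uniform 0-7, cuts 3/5):* the loss is 8.9 points at 95% and 3.5 at 99%.
- *Low reference power (uniform 3-7, cuts 3/5, r = 0.10):* 41.1% against 32.3%, a loss of 8.8.
- *N=200:* nearly the same losses at the same reference power.

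**Step 6, a step response.** In a simulation of 3,000 trials per setting, benefit jumped at one value of use and was scaled so that the correctly specified 1-df test had 80% power. With the jump exactly at a band edge, the bands had 69-80% power against 29-65% for the average. With the jump half a day off the edge, the figures were 34-58% against 29-65%.

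**The case against.** The strongest objection is that much of the loss comes from a test the plan never names. Section 5.1.2 says only that outcomes are compared; the bands are ordered, and a trend test is a fair reading. For uniform use on 0-7 that cuts the loss from about 16 points to about 6. This stands, but it gives no help where only two bands are occupied, and no trend test is specified.

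A reader might infer that banding always costs at least 10 points, or as much as 50. The documents support neither. Losses below 10 appear with a trend test, with clustered use, and at high or low reference power. A loss of 50 needs an assumed distribution with 96% of subjects in the top band and cuts at 2.5 and 4.5; with cuts at 3 and 5 that same distribution gives 48% power rather than 29%.

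A reader might also infer that the lowest band is empty. The screen-failure rule acts at week 4, and section 7.10 leaves later withdrawal for continued noncompliance to the investigator, so the band is thinned but not necessarily emptied over 52 weeks.

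Four further points narrow the remedy without removing the concern:

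- Table 1 scores prescribed care, while section 7.10 applies it to device use, so the quantity to be averaged is not settled.
- Outcomes include counts, binary skin signs and ordinal grades; the calculations cover only normal outcomes.
- No averaging window is given, although outcomes fall at 12, 24 and 52 weeks.
- Compliance is self-selected behaviour after baseline. A complication can add to utilization and also interrupt device use. More power for such an association does not make it causal, and a per-day figure can be over-read.

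A step exactly at a band edge would favour the bands, and the documents do not say which shape holds.

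**Conclusion.** The concern holds as a conditional one. The only planned compliance analysis uses three bands, discards within-band information already collected, and may reduce to nearly a two-group split. For a gradual response at N=300, two-sided 5% and about 80% power for the continuous analysis, the loss is typically about 12-20 points unordered, more under strong skew. With a trend test on three occupied bands cut at 3 and 5, it is about 3-12. No lower bound can be derived, because test, effect size and distribution of use are all unstated. The comparison is secondary and non-randomised, so this is a cheap improvement to the plan and not a threat to the primary endpoints.

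**What to change.** In section 5.1.2, make the main compliance analysis a regression of each outcome on average days per week as a continuous covariate, and specify:

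- **The average:** taken from training to that outcome's time point. State whether it counts Flexitouch use or all prescribed care; sections 5.1.2 (Table 1) and 7.10 must be reconciled on this.
- **The model:** linear for QoL and circumference change, a count model for health care utilization, logistic or ordinal for skin signs and grades.
- **The report:** the association per additional day per week with its 95% CI, described as a non-randomised association.
- **The shape:** one pre-stated curvature check, such as a quadratic or restricted cubic spline term.
- **The bands:** Table 1 kept as a descriptive and supportive comparison.

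The cost is protocol and SAP wording; no new data, visits or subjects are needed. The downside is the near-linearity assumption. If benefit jumps at a band edge, the regression has less power than the bands. The curvature check and the retained band comparison are there to reveal that, although the power of the curvature check has not been calculated.

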5.2 Subject Selection

5.2.1 Inclusion Criteria

1. Age 18 or older
2. Diagnosis of primary or secondary, unilateral or bilateral, LE lymphedema
3. Ability and willingness to participate in all aspects of the study including following prescribed care
4. Ability to provide informed consent
5. Must have a prescription for the Flexitouch (Flexitouch system or Flexitouch Plus)

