3.0 Introduction

3.1 Background and Rationale

The purpose of this study is to evaluate the effect of an advanced pneumatic compression device in improving symptoms and quality of life in patients with lower extremity lymphedema.

Lymphedema is a chronic and disfiguring disease usually secondary to excessive fluid and protein accumulation in the interstitium as result of lymphatic system obstruction.¹ It can occur either primarily (as a result of congenital malformations)

or secondarily (as a result of trauma to the lymphatic system, surgery, radiation therapy, obesity and chronic venous insufficiency).^{2,3} This leads to limb swelling in early stages with progression to thickening skin and fibrosis leaving the affected extremity susceptible to skin breakdown and repeated infections. There is no cure for lymphedema, and the available treatment modalities consist of manual lymphatic drainage, compression therapy, and in very severe cases lymphatic exchange, a costly and invasive procedure.⁴

Pneumatic Compression Devices (PCDs) offer a novel modality for treatment of lymphatic obstruction. The Flexitouch[®] System and Flexitouch[®] Plus are PCDs that target all major lymphatic beds and release pressure in a systematic manner, mimicking a functional drainage system.⁵ Prior studies demonstrated improvement in control of edema and ease of use; however improvement in quality of life (QoL) and decrease in symptoms has not been thoroughly evaluated.^{6,7,8} Therefore we propose to demonstrate improved QoL and symptoms in patients with lower extremity (LE) lymphedema.

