5.1 Study Endpoints

5.1.1 Primary Endpoints

The following primary endpoints for this study will compare changes after 12 weeks of treatment to baseline for the following parameters:

- QoL
- Lymphedema symptoms

In addition, the number of occurrences after 52 weeks of treatment will be compared to the number of occurrences in the year preceding treatment for the following variable:

- Lymphedema and venous related health care utilization

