5.2.2 Exclusion Criteria

1. Diagnosis of active or recurrent cancer, or less than 3 months at the time of initial evaluation from the completion of chemotherapy, radiation therapy or primary surgery for the treatment of cancer.
2. Active skin or limb infection/inflammatory disease (acute cellulitis, or other uncontrolled skin or untreated inflammatory skin disease)
3. Acute thrombophlebitis (in last 2 months)
4. Pulmonary embolism within the previous 6 months
5. Deep Vein Thrombosis (DVT) within the previous 3 months
6. Severe peripheral artery disease (critical limb ischemia including ischemic rest pain, arterial wounds, or gangrene)
7. Pulmonary edema
8. Heart failure (acute pulmonary edema, decompensated acute heart failure)
9. Patients with poorly controlled asthma
10. Previous use of the study PCD

11. Currently using multi-layer bandaging (MLB) unless bandages can be removed for limb circumference measurements
12. Pregnant women or women of childbearing potential not on contraception
13. Any condition where increased venous and lymphatic return is undesirable
14. Currently participating in another medical device or drug clinical trial
15. Signs of noncompliance at the week 4 visit, including: using the device less than 3 times per week and/or not attending the scheduled visit

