7.2 Demographics & Medical History

Demographics will be collected at baseline including the date of birth, ethnicity, race, gender, and employment status.

If the subject is female and of childbearing potential, a urine pregnancy test will be performed to ensure the subject is not pregnant. Per exclusion criterion 11, if a subject is pregnant or a women of childbearing potential not on contraception, they will be excluded from the study.

Significant medical history and lymphedema history will be collected at baseline including number of lymphedema and venous related visits that required health care utilization (HCU) (includes clinic visits, hospitalization, walk-in clinic/urgent care, and ER visits).

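### The primary utilization endpoint compares 52 weeks of treatment with a fixed prior year, although eligible subjects may have developed or been diagnosed with lymphedema within that year

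*Combined protocol and SAP*

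**What the plan says.** Section 5.1.1 lists "Lymphedema and venous related health care utilization" as a primary endpoint and states the contrast: "the number of occurrences after 52 weeks of treatment will be compared to the number of occurrences in the year preceding treatment". Both windows have a fixed length, and neither depends on how long the subject has had the disease.

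On disease history, section 5.2.1 requires only "Diagnosis of primary or secondary, unilateral or bilateral, LE lymphedema". The other inclusion criteria concern age, willingness, consent and a device prescription. None of the 15 exclusions in section 5.2.2, and neither of the payer conditions in section 8.0, sets a minimum time since onset or diagnosis. The nearest to one is exclusion 1, which bars subjects "less than 3 months at the time of initial evaluation from the completion of chemotherapy, radiation therapy or primary surgery for the treatment of cancer". It limits how recent cancer treatment may be, not how recent the lymphedema may be. Section 3.1 names surgery, radiation therapy and trauma among the causes of secondary disease.

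The prior count comes from the history in section 7.2: "Significant medical history and lymphedema history will be collected at baseline including number of lymphedema and venous related visits". That section does not name an onset or diagnosis date. Section 5.0 describes a single-arm study. Section 13.1 gives no method, and so no restriction, offset or stratification by disease duration.

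**The concern.** A before/after count in the same subjects is a fair contrast only if both windows expose the subject to the same risk of a countable visit. A subject whose lymphedema began part-way through the prior year could have lymphedema visits for only part of that year, but for all 52 weeks of follow-up. With no device effect, such a subject's count tends to rise. A subject diagnosed within that year may instead have a cluster of diagnostic and work-up visits in the prior window, and the count then tends to fall. In both cases the change is produced by where the subject stands in the course of the disease.

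At stake is the reading of one primary endpoint: a real reduction could be hidden, or an apparent one created, with no control group to show which. Section 5.1.2 also compares primary outcomes across compliance categories, so the same component enters those contrasts. The problem would remain with perfect recall of prior visits, no gap between screening and training, and no regression to the mean.

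**Working it through.** **The plan's own figure.** There is none to reproduce for this endpoint. Section 13.2 gives up to 300 subjects as a convenience sample, with no visit rate, effect size, error rate or power.

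**Inputs.** From section 5.1.1: a 12-month prior window and a 52-week follow-up, treated as equal. Assumed, because the documents give no figures: the share p of subjects with recent onset, the months m of disease at Day 0, and the visit rates. Throughout, the device has no effect and the visit rate is constant while the subject has the disease.

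**Case A: no countable visits before onset.**

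Prior count as a fraction of a full diseased year = (1 − p) + p × m/12. Spurious follow-up/prior ratio = 1 / that fraction. With m = 4:

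| p | Prior fraction | Ratio |
|---|---|---|
| 10% | 0.90 + 0.10 × 4/12 = 0.933 | 1.07 |
| 20% | 0.80 + 0.20 × 4/12 = 0.867 | 1.15 |
| 30% | 0.70 + 0.30 × 4/12 = 0.800 | 1.25 |

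At p = 20%, a true ratio of 0.87 would appear as 0.87 / 0.867 = 1.00.

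**Case B: the pre-onset rate is half the later rate.** The endpoint also counts venous related visits, and section 3.1 lists chronic venous insufficiency among the causes, so visits before onset need not be zero.

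Prior fraction = (1 − p) + p × (4/12 + 0.5 × 8/12) = (1 − p) + p × 8/12.

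| p | Prior fraction | Ratio |
|---|---|---|
| 10% | 0.967 | 1.03 |
| 20% | 0.933 | 1.07 |
| 30% | 0.900 | 1.11 |

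**Case C: work-up visits cluster before treatment.** Assume 2 visits a year, no other visits before onset, p = 30%, m = 3, and 3 extra diagnostic visits per recent-onset subject.

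Mean prior count = 0.70 × 2 + 0.30 × (2 × 3/12 + 3) = 1.40 + 1.05 = 2.45. Ratio = 2 / 2.45 = 0.82.

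The two effects cancel when the extra visits equal 2 × (1 − 3/12) = 1.5 per recent-onset subject. Above that, the bias favors the device.

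**After restriction.** If every subject has had the disease for at least 12 months at Day 0, the prior fraction in Cases A and B is 1 and the no-effect ratio is 1.00. Case C also returns to 1.00 if the work-up visits fall before the diagnosis date or close to it, outside the prior year.

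**The case against.** The strongest reply is that nothing shows recent-onset subjects to be numerous. Section 3.1 describes a chronic disease, the LYMQOL in section 7.9 is designed for chronic edema, and no duration distribution is given. This stands, and it is why the figures are a range under assumptions.

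A reader might infer from exclusion 1 that very recent disease is expected, with about 9 of the 12 comparator months free of it. The text does not support that. The criterion sets a 3-month floor after cancer treatment, so it shows only that such a subject is permitted. The clock runs from completion of chemotherapy, radiation or primary surgery, so surgery that caused the lymphedema may lie well before the last treatment. The 9-month picture needs the last treatment to be the cause, to be just over 3 months old, and to follow no earlier lymphedema. Even without cancer, the prior year is mostly free of disease only when onset is less than 6 months before treatment.

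A second reply is that venous related visits can occur before onset. This also stands; Case B shows that it shrinks the bias without removing it.

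A third is that this is one instance of the missing analysis method in section 13.1. That is only partly right. Section 5.1.1 does state the comparison, and following it as written gives the mismatch.

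A fourth is that the case report form is not among the documents and may already capture a date. It may, but no section uses such a date in this comparison.

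**Conclusion.** The point holds as a flaw in the stated comparison of section 5.1.1. The plan permits subjects whose lymphedema began or was diagnosed within the comparator year, and it has neither a control arm nor an adjustment to separate time since onset from treatment.

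The size is unknown. For 10% to 30% of subjects with 4 months of disease, the no-effect ratio is 1.07 to 1.25 with no visits before onset and 1.03 to 1.11 with a half-rate before onset. It falls to about 0.82 in the work-up example. The shares, durations and rates are all assumptions.

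A reader might infer that the bias always works against the device, so that any reduction seen is conservative. The documents do not fix the direction, so that cannot be claimed. Nor does it follow that eligibility is wrong: the diagnosis criterion can serve the quality-of-life and symptom endpoints as it stands. The change should be made, but the documents do not show that the endpoint is invalid without it.

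**What to change.** Leave section 5.2.1 unchanged.

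- **Section 7.2:** record the date of lymphedema diagnosis in the baseline lymphedema history, and the date of symptom onset where it is known.
- **Section 5.1.1:** make the primary before/after utilization comparison in subjects diagnosed at least 12 months before Day 0. Report the all-subject comparison alongside it, and show subjects of shorter duration separately as a rate per month since diagnosis.

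The rule should use one date. Diagnosis is the easier to document, since section 7.4.3 includes a latent stage with no clinical signs and onset can be hard to place. Onset cannot follow diagnosis, so a diagnosis at least 12 months old means the disease was present throughout the prior year.

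The cost is one or two date fields and a few sentences, with no change to enrolment or visits. For subjects of shorter duration, the visit count must also be taken from the diagnosis date. The main downside is fewer subjects in the primary utilization comparison, including some with long-standing but newly diagnosed disease; the all-subject report keeps them in view. No power calculation is disturbed, because the sample size rests on none. If few subjects prove to be recently diagnosed, the recorded date will show it.
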